6.12.4. Other Secondary and Exploratory Efficacy Analyses

Other secondary and exploratory efficacy measures will be summarized by treatment and nominal visit. Statistical analyses will be conducted in a manner similar to Sections 6.12.1 and 6.12.2.

Table GPHO.6.2. Secondary and Exploratory Efficacy Measures Not Controlled for Type 1 Error

Objective	Relative to the efficacy measure:	Analysis Conducted in a manner similar to:	Additional Information
Secondary Analyses			
once-weekly tirzepatide 5 mg, 10 mg, and/or 15 mg is superior to insulin glargine at 40 weeks	Change from baseline in fasting serum glucose (central laboratory)	6.12.1.1	Use baseline HbA1c strata as a fixed effect in place of baseline HbA1c as a covariate. Use baseline FSG as a covariate. LSM estimates will be plotted by treatment and visit.
	Proportion of patients achieving an HbA1c target value of $\leq 6.5\%$ (48 mmol/mol),	6.12.2.3	None
	Proportion of patients achieving an HbA1c target value of $< 5.7\%$ (39 mmol/mol).	6.12.2.3	None
	Change from baseline in 7-point self-monitored blood glucose (SMBG) profiles	6.12.1.1	Use baseline HbA1c strata as a fixed effect in place of baseline HbA1c as a covariate. Use baseline SMBG as a covariate. LSM estimates at 40-weeks will be plotted by treatment and 7-points. In addition to the analyses on each of the 7-points, similar analyses will be done for the 2-hour morning, midday, and evening meal excursions, the mean of all meals 2-hour excursion, the mean of all 7-point measurements, the mean of all pre-meal measurements, and the mean of all 2-hour postprandial measurements.
	Proportion of patients achieving weight loss of $\geq 5\%$, from baseline	6.12.2.3	Use baseline HbA1c strata as a fixed effect in place of baseline HbA1c as a covariate and baseline weight as a covariate

	Proportion of patients achieving weight loss of $\geq 10\%$ from baseline	6.12.2.3	Use baseline HbA1c strata as a fixed effect in place of baseline HbA1c as a covariate and baseline weight as a covariate
	Proportion of patients achieving weight loss of $\geq 15\%$ from baseline	6.12.2.3	Use baseline HbA1c strata as a fixed effect in place of baseline HbA1c as a covariate and baseline weight as a covariate
To compare tirzepatide 5 mg, 10 mg, and 15 mg to insulin glargine at 40 weeks	The various Diabetes Treatment Satisfaction Questionnaire change (DTSQc) scores (see Section 6.17.4 for more details).	6.12.1.2 CCI	Use baseline HbA1c strata as a fixed effect in place of baseline HbA1c as a covariate. Use baseline DTSQs score as a covariate.
Exploratory Analyses			
To compare tirzepatide 5 mg, 10 mg, and 15 mg with insulin glargine for the following:	Change from baseline in lipid parameters (total cholesterol, HDL, non-HDL, VLDL, TG).	6.12.1.1	Use baseline HbA1c strata as a fixed effect in place of baseline HbA1c as a covariate. Use corresponding baseline lipid parameter as a covariate.
	Change from baseline in BMI.	6.12.1.1	Use baseline HbA1c strata as a fixed effect in place of baseline HbA1c as a covariate. Use corresponding baseline BMI as a covariate.
	Change from baseline in waist circumference.	6.12.1.1	Use baseline HbA1c strata as a fixed effect in place of baseline HbA1c as a covariate. Use corresponding baseline waist circumference as a covariate.
	Changes from baseline in the European Quality of Life – 5 dimensions (EQ-5D-5L) index and visual analog scale (VAS) scores.	6.12.1.2	Use baseline HbA1c strata as a fixed effect in place of baseline HbA1c as a covariate. Use baseline EQ-5D-5L score as a covariate.
	Changes from baseline in the Impact of Weight on Self-Perceptions Questionnaire (IW-SP) scores.	6.12.1.2	Use baseline HbA1c strata as a fixed effect in place of baseline HbA1c as a covariate. Use baseline IW-SP score as a covariate.
	Changes from baseline in the Ability to Perform Physical Activities of Daily Living (APPADL) scores.	6.12.1.2	Use baseline HbA1c strata as a fixed effect in place of baseline HbA1c as a covariate. Use baseline APPADL score as a covariate.

To compare tirzepatide 5 mg, 10 mg, and 15 mg with insulin glargine for the following:	Proportion of patients achieving an HbA1c target $\leq 6.5\%$, without weight gain (<0.1 kg), and without documented symptomatic hypoglycemia or severe hypoglycemia	6.12.2.3	Include baseline body weight as additional covariate
	Proportion of patients achieving an HbA1c target $<7.0\%$, without weight gain (<0.1 kg), and without documented symptomatic hypoglycemia or severe hypoglycemia	6.12.2.3	Include baseline body weight as additional covariate
	Proportion of patients achieving an HbA1c target $\leq 6.5\%$, without weight gain (<0.1 kg), and without clinically significant documented symptomatic hypoglycemia or severe hypoglycemia	6.12.2.3	Include baseline body weight as additional covariate
	Proportion of patients achieving an HbA1c target $<7.0\%$, without weight gain (<0.1 kg), and without clinically significant documented symptomatic hypoglycemia or severe hypoglycemia	6.12.2.3	Include baseline body weight as additional covariate
	Proportion of patients achieving an HbA1c target $<7.0\%$, weight loss $\geq 5\%$, and without clinically significant documented symptomatic hypoglycemia or severe hypoglycemia	6.12.2.3	Include baseline body weight as additional covariate

Abbreviations: HbA1c = hemoglobin A1c; QW = once-weekly.

6.13. Safety Analysis

Unless specified otherwise, safety assessments will be based on the SS ([Table GPHO.6.1](#)). All events that occur between the date of first dose of study drug to the date of patient's safety follow-up visit or patient's end of study participation will be included, regardless of the adherence to study drug or initiation of rescue therapy. The events occurring on the day of the first dose of study medication will be counted as post-treatment. For assessing benefit and risk profile through 40-weeks, selected safety analyses will be conducted by utilizing safety data from first dose through the date of 40-week visit. Some safety analyses may be conducted after excluding data after the initiation of new antihyperglycemic therapy. Unless specified otherwise, statistical assessment of homogeneity of the distribution of categorical safety responses among treatment arms will be conducted using Fisher's exact test.

The mean change from baseline difference among treatment at all scheduled visits will be assessed via a MMRM using REML. The model will include country, baseline HbA1c ($\leq 8.5\%$, $> 8.5\%$ [≤ 69 , > 69 mmol/mol]), baseline concomitant oral antihyperglycemic medication, treatment group, visit, and treatment-by-visit interaction as fixed effects, and baseline value of the safety parameter as a covariate. To model the covariance structure within patients, the unstructured covariance matrix will be used. If this model fails to converge, the covariance structures will be tested in order specified in Section 6.12.1.1.

For selected safety parameters, time-to-first-event analysis via the cox-proportional hazards model may be conducted. Patients without the event will be censored at the end of study participation. For patients experiencing the event, the “time-to-first-event” will be the time (in days) from first dose to first occurrence of the event.

Where necessary, the rate of events will be analyzed using a generalized linear mixed-effects model assuming the number of events follow a negative binomial distribution, and with treatment as a fixed effect. The logarithm of days during the active treatment period will be adjusted as an offset to account for possible unequal treatment duration of follow-up between patients.

6.13.1. Adverse Events

A TEAE is defined as an event that first occurred or worsened in severity after baseline. The MedDRA Lowest Level Term (LLT) will be used in the treatment-emergent derivation. The maximum severity for each LLT during the baseline period including ongoing medical history will be used as baseline severity. For events with a missing severity during the baseline period, it will be treated as ‘mild’ in severity for determining treatment-emergence. Events with a missing severity during the postbaseline period will be treated as severe and treatment-emergence will be determined by comparing to baseline severity.

The percentages of patients with TEAEs will be summarized by treatment using MedDRA PT nested within SOC. Statistical comparisons will be applied at both the SOC and PT levels. Events will be ordered by decreasing frequency within SOC. For events that are sex-specific, the denominator and computation of the percentage will include only patients from the given sex.

An overview of the number and percentage of patients who experienced a TEAE, serious adverse event (SAE), died due to an AE, discontinued from study treatment, or study due to an AE, relationship to study drug, and outcome of AE, will be summarized by treatment.

The percentages of patients with TEAEs, overall and common (common TEAEs occurred in $\geq 5\%$ of patients before rounding), will be summarized by treatment using MedDRA PT. Events will be ordered by decreasing frequency.

The percentages of patients with TEAEs by maximum severity will be summarized by treatment using MedDRA PT. For each patient and TEAE, the maximum severity for the MedDRA PT is the maximum postbaseline severity observed from all associated LLTs mapping to the MedDRA PT. The maximum severity will be determined based on the non-missing severities. If all

severities are missing for the defined postbaseline period of interest, it will show as missing in the table. Only counts and percentages will be included for the TEAEs by maximum severity.

Patient narratives will be provided for all patients who experience any of the following “notable” events:

- Death
- SAE
- Permanent discontinuations of study or study treatment due to AE
- Pregnancy
- Adjudication Confirmed Major Adverse Cardiovascular Events
- Adjudication Confirmed Pancreatitis

6.13.1.1. Deaths

A listing of all deaths will be provided. The listing will include patient identification including the treatment, site number, date of death, age at the time of enrollment, sex, MedDRA PT of associated AE, time from first dose of study drug to death, time from last dose of study drug to death (if patient had discontinued study drug), investigator reported cause of death, and CEC adjudicated cause of death.

6.13.1.2. Other Serious Adverse Events

The number and percentage of patients who experienced an SAE (including deaths and SAEs temporally associated or preceding deaths) during the study follow-up will be summarized by treatment using MedDRA PT nested within SOC. Events will be ordered by decreasing frequency within SOC.

A listing of all SAEs will be provided. The listing will include treatment, patient identification including the site number, date of event, age at the time of enrollment, sex, MedDRA SOC and PT, severity, action taken, outcome, relationship to study drug, time from first dose of study drug to the event, and event duration.

6.13.1.3. Discontinuation from Study Due to Adverse Event

The number and percentage of patients who prematurely discontinue the study due to an AE will be summarized by treatment using MedDRA PT nested within SOC. Events will be ordered by decreasing frequency within SOC.

6.13.1.4. Discontinuation from Study Drug Due to Adverse Event

The number and percentage of patients who prematurely discontinue study drug due to an AE will be summarized by treatment using MedDRA PT nested within SOC. Events will be ordered by decreasing frequency within SOC. Time-to-event analyses will be conducted by treatment on time to study drug discontinuation as well as on time to study drug discontinuation due to an AE.

6.13.2. Special Safety Topics

6.13.2.1. Hypoglycemic Events

Definitions of different categories of hypoglycemic events are included in [Table GPHO.6.3](#).

Table GPHO.6.3. Definitions of Hypoglycemic Event Categories

	Symptoms and/or Signs of Hypoglycemia	Blood Glucose Level
Documented symptomatic hypoglycemia	Yes	≤70 mg/dL (3.9 mmol/L)
Documented asymptomatic hypoglycemia	No	≤70 mg/dL (3.9 mmol/L)
Documented unspecified hypoglycemia	Unknown	≤70 mg/dL (3.9 mmol/L)
Clinically significant documented symptomatic hypoglycemia	Yes	<54 mg/dL (3.0 mmol/L)
Clinically significant documented asymptomatic hypoglycemia	No	<54 mg/dL (3.0 mmol/L)
Clinically significant documented unspecified hypoglycemia	Unknown	<54 mg/dL (3.0 mmol/L)

Severe hypoglycemia: Defined as an episode with severe cognitive impairment requiring the assistance of another person to actively administer carbohydrate, glucagon, or other resuscitative actions. Severe hypoglycemia will be reported as an SAE. Severe hypoglycemia will be considered an adverse event of special interest (AESI).

Nocturnal hypoglycemia: Defined as any hypoglycemic event that occurs between bedtime and waking.

To avoid duplicate reporting, all consecutive BG values ≤70 mg/dL (3.9 mmol/L) occurring within a 1-hour period may be considered to be a single hypoglycemia event.

Statistical summaries and analyses will exclude hypoglycemic events occurring while on rescue therapy. For each of the aforementioned hypoglycemia categories, incidence as well as rate per patient year of exposure will be provided by treatment. A listing of hypoglycemic events occurring while on rescue therapy will also be provided.

For each of the hypoglycemia categories mentioned above, the incidence of any hypoglycemic event with blood glucose ≤70 mg/dL [3.9 mmol/L] or <54 mg/dL [3.0mmol/L]) will be analyzed using logistic regression with treatment, country, and baseline concomitant oral antihyperglycemic medication as fixed effects, and baseline HbA1c and rate of hypoglycemic events at baseline as covariates. The rate of hypoglycemic episodes will be analyzed using a generalized linear mixed-effects model assuming the number of hypoglycemic episodes follows a negative binomial distribution with the mean modeled using country, baseline concomitant oral antihyperglycemic medication use, and treatment as a fixed effects and baseline HbA1c as a covariate. The logarithm of days during the active treatment period will be adjusted as an offset to account for possible unequal treatment duration of follow up between patients.

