
Safety
 
 To compare tirzepatide 5 mg, 10 mg, and 15 mg to titrated insulin glargine for: 	
 Treatment-emergent adverse events (TEAEs) Early discontinuation of study drug due to adverse events (AEs) Adjudicated pancreatic AEs Serum calcitonin Incidence of allergic and hypersensitivity reactions Incidence of treatment-emergent anti-drug antibodies to tirzepatide Mean change in systolic and diastolic blood pressure and pulse rate from baseline Occurrence of hypoglycemic events Incidence of initiation of rescue therapy for severe persistent hyperglycemia

Summary of Study Design:

Study GPHO is a phase 3, multicenter, randomized, open-label, parallel-group study to compare the efficacy and safety of 3 maintenance doses of tirzepatide with titrated insulin glargine in patients with T2DM who have inadequate glycemic control on stable doses of metformin with or without a sulfonylurea (Figure GPHO.1).

Treatment Groups and Duration:

Study GPHO will consist of 3 periods: an approximately 3-week screening/lead-in period, followed by a 40 week treatment period, and a 4-week safety follow-up period. Patients will be randomized in a 1:1:1:1 ratio (tirzepatide 5 mg, 10 mg and 15 mg QW, and insulin glargine QD). Patients will be stratified at randomization based on HbA1c ($\leq 8.5\%$, $> 8.5\%$ [69 mmol/mol]), country and use of concomitant oral antidiabetic treatments (Metformin alone, metformin plus a sulfonylurea).

Number of Patients:

A total of approximately 956 patients will be randomized in a 1:1:1:1 ratio to tirzepatide doses: 5 mg QW (239 patients), 10 mg QW (239 patients), 15 mg QW (239 patients), and insulin glargine QD (239 patients).

Statistical Analysis:

Efficacy Analyses:

Efficacy and safety will be assessed using the modified intent-to-treat (mITT) population, which consists of all randomly assigned participants who are exposed to at least one dose of study drug. The primary efficacy assessment will be performed on data obtained before the initiation of any rescue therapy and before premature treatment discontinuation. The analysis model for change from baseline in HbA1c assessed over time will be a mixed-model for repeated measures (MMRM), with terms: treatment, visit, and treatment-by-visit interaction, stratification factors:

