9.2.2. Adverse Events of Special Interest

9.2.2.1. Hypoglycemia

Patients will collect information on episodes of hypoglycemia after signing ICF until the last study visit (Follow up Visit or Early Termination Visit). For that purpose, patients will be trained about signs and symptoms of hypoglycemia, how to treat hypoglycemia, and how to collect appropriate information for each episode of hypoglycemia in the study according to the Schedule of Activities. Site personnel will enter this information into the eCRF hypoglycemia page at each visit.

Investigators should use the following definitions and criteria when diagnosing and categorizing an episode considered to be related to hypoglycemia: (the PG values in this section refer to values determined by a laboratory or International Federation of Clinical Chemistry and Laboratory Medicine plasma-equivalent glucose meters and strips) (ADA 2017):

Glucose Alert Value (Level 1):

- **Documented symptomatic hypoglycemia** is defined as any time a patient feels that he or she is experiencing symptoms and/or signs associated with hypoglycemia, and has a PG level of ≤ 70 mg/dL (≤ 3.9 mmol/L).
- **Documented asymptomatic hypoglycemia** is defined as any event not accompanied by typical symptoms of hypoglycemia, but with a measured PG ≤ 70 mg/dL (≤ 3.9 mmol/L).
- **Documented unspecified hypoglycemia** is defined as any event with no information about symptoms of hypoglycemia available, but with a measured PG ≤ 70 mg/dL (≤ 3.9 mmol/L).

Clinically Significant Hypoglycemia (Level 2):

- **Documented symptomatic hypoglycemia** is defined as any time a patient feels that he/she is experiencing symptoms and/or signs associated with hypoglycemia, and has a PG level of < 54 mg/dL (< 3.0 mmol/L).
- **Documented asymptomatic hypoglycemia** is defined as any event not accompanied by typical symptoms of hypoglycemia, but with a measured PG < 54 mg/dL (< 3.0 mmol/L).
- **Documented unspecified hypoglycemia** is defined as any event with no information about symptoms of hypoglycemia available, but with a measured PG < 54 mg/dL.

(<3.0 mmol/L).

Severe hypoglycemia (Level 3):

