10.3.4.1. Hypoglycemic Events

Incidence of documented symptomatic hypoglycemia events and severe hypoglycemia in each category (either total or nocturnal) will be compared between tirzepatide doses and insulin glargine using negative binomial regression analysis. Selected safety analyses may be conducted excluding data after introducing another anti-hyperglycemic therapy (for example, rescue therapy).

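### SAP 6.13.2.1 leaves the baseline hypoglycemia rate out of the negative binomial rate model although the adjacent incidence model uses it: a small, nearly free gain in precision forgone, with no bias

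*SAP*

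**What the plan says.** SAP 6.13.2.1 gives the two models in consecutive sentences.

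- Incidence is analyzed by logistic regression with treatment, country and baseline oral medication as fixed effects, and "baseline HbA1c and rate of hypoglycemic events at baseline as covariates".
- The event rate is analyzed by a negative binomial model with its "mean modeled using country, baseline concomitant oral antihyperglycemic medication use, and treatment as a fixed effects and baseline HbA1c as a covariate". Exposure enters through an offset: "The logarithm of days during the active treatment period will be adjusted as an offset".

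Elsewhere the plan asks for less. The general rate model in SAP 6.13 is specified as "assuming the number of events follow a negative binomial distribution, and with treatment as a fixed effect". Protocol 10.3.4.1 says that hypoglycemic events "will be compared between tirzepatide doses and insulin glargine using negative binomial regression analysis" and names no covariates.

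Lead-in data are collected. Protocol 9.2.2.1 states: "Patients will collect information on episodes of hypoglycemia after signing ICF until the last study visit". The Protocol synopsis describes "an approximately 3-week screening/lead-in period". Protocol 5.1 issues the glucose meter and diary, with training, at Visit 2 (Week -2). Neither document defines the baseline hypoglycemia rate. The general rule in SAP 6.2, the last available measurement, does not define a rate.

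**The concern.** The two models describe the same events in the same patients, yet one adjusts for prior hypoglycemia and the other does not. If either were to have the term, the count model is the more natural place. A yes/no outcome discards repeat episodes, while a count keeps them, and repeat episodes are where patients differ most. A covariate that explains part of that spread lowers the variance of the log rate ratio.

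What is at stake is efficiency only. Under randomization, omitting a prognostic covariate leaves the comparison of rates valid. Hypoglycemia is of real interest here, because the Protocol's rationale describes it as a known drawback of glargine. The SAP reports incidence and rate side by side, so a difference in adjustment should have a reason.

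**Working it through.** **Figures in the plan.** There is none to reproduce on this point. The documents give no rate, dispersion, power or sample size for hypoglycemia; the planned 956 patients were sized on HbA1c. Every hypoglycemia rate below is assumed.

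**Covariate sets side by side (SAP 6.13.2.1).**

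| Term | Incidence (logistic) | Rate (negative binomial) |
|---|---|---|
| Treatment | yes | yes |
| Country | yes | yes |
| Baseline oral medication | yes | yes |
| Baseline HbA1c | yes | yes |
| Baseline hypoglycemia rate | yes | no |

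**Simulation 1: best case.** Two arms of 239, 21-day lead-in, 280 days of follow-up, rate ratio 2, gamma frailty with shape 0.3 or 0.6. Lead-in events occur at the full underlying rate with the same patient frailty as later. The model is fitted with and without log(lead-in count + 0.5). Ratio of mean model-reported variances, with / without (150 trials per cell):

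- 0.3 events per patient-year: 0.982 and 0.995, a reduction of 0.5 to 2%.
- 1 per year: 0.935 and 0.968, a reduction of 3 to 7%.
- 3 per year: 0.821 and 0.885, a reduction of 12 to 18%.

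A repeat with 1,500 trials per cell gave 0.821 and 0.886 at 3 per year, and 0.927 and 0.964 at 1 per year. It also recorded the spread of the estimates themselves. The SD ratios were 0.957 and 0.961 at 3 per year. The true variance therefore falls by 1 - 0.957² = 8.4% and 1 - 0.961² = 7.6%. At 1 per year the SD ratios of 0.985 and 0.989 give 3.0% and 2.2%. The model-reported gain overstates the real one.

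**Simulation 2: lower lead-in rates.** Two arms of 239, 40 weeks, 10% of patients with shortened follow-up, rate ratio 0.5, dispersion 3 (4 at 6 per year), 300 trials per cell. The covariate is the lead-in rate. The country, oral-medication and HbA1c terms were left out. Model variance reduction = 1 - (SE ratio)².

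| Glargine rate per year | Lead-in rate, % of glargine rate | Window (weeks) | Correlation | Patients with any lead-in event | SE ratio | Model variance reduction | Empirical SD ratio |
|---|---|---|---|---|---|---|---|
| 1 | 10 | 2 | 0.5 | 0.4% | 1.000 | 0.0% | 0.997 |
| 1 | 50 | 2 | 0.5 | 1.9% | 0.999 | 0.2% | 1.012 |
| 1 | 50 | 3 | 1.0 | 2.7% | 0.986 | 2.8% | 0.978 |
| 3 | 10 | 2 | 0.5 | 1.0% | 0.998 | 0.4% | 1.013 |
| 3 | 30 | 3 | 0.7 | 4.6% | 0.986 | 2.8% | 0.999 |
| 6 | 10 | 2 | 0.5 | 2.1% | 0.998 | 0.4% | 0.995 |
| 6 | 30 | 3 | 0.7 | 8.4% | 0.971 | 5.7% | 1.005 |
| 3 | 100 | 3 | 0.7 | 13.0% | 0.961 | 7.6% | 0.976 |
| 3 | 100 | 3 | 1.0 | 13.2% | 0.915 | 16.3% | 0.932 |
| 6 | 100 | 3 | 1.0 | 19.5% | 0.848 | 28.1% | 0.944 |

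A yes/no indicator of any lead-in event gave SE ratios within 0.01 of these. Mean log rate ratios with and without the term differed by 0.01 or less, so there is no sign of bias. In the last row the model-reported 28.1% corresponds to 1 - 0.944² = 10.9% in the estimates.

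**Simulation 3: 14-day window.** With a lead-in rate 30 to 50% of the on-treatment rate (500 trials per cell), the model variance fell by about 1 to 5%. The empirical variance ratio was 0.94 to 1.01, and confidence-interval coverage was maintained.

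**Which settings are plausible.** Patients are insulin-naive with HbA1c of at least 7.5% (Protocol 6.1). Severe hypoglycemia within the previous 6 months is an exclusion (Protocol 6.2). Meters arrive at Visit 2, so about 14 days are meter-supported. Few lead-in events are likely; that is an inference, not a figure in the documents.

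**Why the window matters.** One event is 365/21 = 17.4 per year over 21 days, but 365/14 = 26.1 per year over 14 days.

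**The case against.** The strongest reply is that this is covariate preference. The rate model already adjusts for more than the SAP's general rate model or the Protocol's description, so no text is contradicted. It already includes baseline oral medication, which captures sulfonylurea use, an obvious source of heterogeneity. With a short lead-in and few events, the real gain may be undetectable. All of this stands, and it is why the point is minor. It does not explain why the term belongs in the incidence model alone.

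A reader might also infer stronger claims that the documents do not support:

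- That the trial's main safety contrast is weakened. SAP 4.4 lists hypoglycemia among nine unranked safety objectives, and SAP 6.6 applies no multiplicity control to safety.
- That matching covariates would make the incidence and rate results comparable. One is an odds ratio and the other a rate ratio; they stay on different scales.
- That the term is free of any downside. SAP 6.13.2.1 covers sparse categories such as severe and nocturnal events, where an extra term could strain convergence.
- That the subgroup models in SAP 6.18.4 need the same edit. That section names no model.

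**Conclusion.** The omission is real and unexplained, and its effect is small. In plausible settings the gain is about 0 to 5% of the variance of the log rate ratio, with one cell at 5.7% under an assumed 6 events per patient-year. A gain of up to about 18% at 3 per year needs lead-in and on-treatment rates to be equal and fully correlated. Even then the estimates themselves gain about 8% in the larger run. The extreme cell at 6 per year goes further on paper, but only to about 11% in the estimates.

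The reading that the rate comparison is biased or invalid does not hold: randomization protects it, and the simulated estimates barely moved. All sizes rest on assumed rates, dispersions and correlations. The conclusion is a free improvement of minor size.

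**What to change.** In SAP 6.13.2.1:

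1. Define baseline hypoglycemia once: one pre-randomization window (for example Visit 2 to randomization, when meters and diaries are in use) and the event category counted.
2. Add that term to the negative binomial rate model, as log(lead-in event count + 0.5) or as a yes/no indicator of any lead-in event. Either form avoids annualizing a single event over a short window.
3. Prespecify that the term is dropped in sparse categories, for example severe or nocturnal events, if the model does not converge.
4. If the sponsor prefers to keep the term in the incidence model only, say why.

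The cost is a few lines of SAP text and one degree of freedom, with possible non-convergence in sparse categories, which step 3 handles. No new data are needed.
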